### **9.1.6 Change in PSA from Baseline to Each Visit**

Change and percent change of PSA from baseline will be summarised by descriptive summary statistics for each treatment arm (median and inter-quartile range) as well as actual values by visit and treatment arm for the analyses set.

## **10 Safety**

Safety parameters will be evaluated for the Safety Analysis Set, see Section 6.1. The primary endpoints, adverse events of special interest and the primary analyses of these are described in Sections 10.4, and 10.5, respectively.

### **10.1 General considerations**

All statistical tests will be performed using a two-sided test at a 5 % significance level.

AEs will be summarized by treatment group, overall as well as in terms of intensity and relationship to study drug. The handling of missing data will be described for each analysis below.

#### **10.1.1 Table Shell for Adverse Events**

To make a balanced comparison with respect to possible differences in drop-out rates, the standard safety table will display the total number (N) of patients exposed, the number of patients reporting an AE, the percentage of patients (%) with an AE, the number of person years, the incidence rate and its 95% CI. The exact uniformly most powerful unbiased test of equal incidence rates will be used to flag significant differences between the two treatment groups.

### **10.2 Definition of Treatment-Emergent Adverse Events**

All adverse events of exposed patients occurring during the “Main Treatment Period” or thereafter (as defined in Section 8) will be considered as treatment-emergent (TE).

Adverse events that occur before first dose (on non-exposed patients) are not defined as treatment emergent and will not be reported.

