#### 3.1 Schedule of Assessments

Patients will be enrolled after the initial decision (by the investigator) has been made to introduce Firmagon or GnRH agonist as per label indication for prostate cancer. Data will be collected at baseline and every 3 months ( $\pm$  4 weeks) for the first 2 years, then every 6 months ( $\pm$  6 weeks) for the remaining 3 years. Firmagon is dosed monthly, while GnRH agonists may be administered less frequently, therefore suggested data collection time points *may not always* coincide with treatment-related clinical visits. If necessary, telephone outreach may be used by sites to collect relevant data. Patients who discontinue ADT therapy will continue to be followed for safety outcomes in order to assess the long term safety associated with ADT.

A flowchart of *recommended* study assessments is provided in [Table 1](#).

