## **6 Analysis Dataset**

As the study is non-randomised the intention to treat principle (analyses according to the planned treatment regimen) will not be followed. All analyses will be performed on the actual (received) treatment.

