## 8 Exposure

One of the objectives in the study is to collect AESIs and compare long-term clinical experience with specific important conditions between Firmagon and agonist therapies. The therapy regimens may change, e.g. from continuous treatment to intermittent, at the discretion of the investigator. This section defines exposure periods that are used in order to be able to make unbiased (continuous) treatment comparisons of treatment-emergent adverse events.

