### 8.1 Exposure Periods

In order to limit bias from different treatment effects and overlapping treatment periods on reported adverse events, and to make data comparable to a greater degree, the total exposure period will be partitioned as follows.

At the Baseline Visit patients will be asked if they are on ADT and if so, when it was initiated. The date of Informed Consent is also recorded as part of the eCRF data collection. Start date of *main treatment period* will be considered to be the date at which both the informed consent has been signed, and the first dose has been administered. End date of main treatment period will be recorded as date of loss to follow-up, change in ADT, discontinuation of ADT, or end-of-trial visit, whatever comes first. If treatment continues after end of main treatment period (e.g. due to regimen change), a consecutive treatment period will be considered to be started. Consecutive treatment periods have a similar definition of end-of treatment period as the main treatment period.

In the case that the informed consent was not signed at time of first dosing, a “pre-consent period” is considered. This period ends when the informed consent is signed, at which time the “Main Treatment Period” starts, see Table 4.

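### The general TEAE tables flag group differences on events pooled across all periods after first treatment, although Section 8 defines exposure periods to avoid this, so the flags may be biased

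*SAP*

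**What the plan says.** Section 8 introduces the exposure periods as a means to "make unbiased (continuous) treatment comparisons of treatment-emergent adverse events". Section 8.1 repeats the reason: "In order to limit bias from different treatment effects and overlapping treatment periods on reported adverse events". It ends the Main Treatment Period at the earliest of loss to follow-up, change in ADT, discontinuation of ADT and the end-of-trial visit. Anything after that belongs to a later period.

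Section 10.2 sets the window for the general tables much wider. All adverse events of exposed patients "occurring during the “Main Treatment Period” or thereafter (as defined in Section 8) will be considered as treatment-emergent". In Section 10.1.1, the standard safety table shows incidence rates per group, and an exact test of equal rates "will be used to flag significant differences between the two treatment groups". Section 10.1 sets the level: "All statistical tests will be performed using a two-sided test at a 5 % significance level".

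Three other places bear on the point:
- Section 10.4.1 restricts AESIs to the Main Treatment Period, for the same bias reason as Section 8.1. No such restriction is stated for the general tables in Sections 10.1.1 to 10.3.2.
- Section 3.1 provides for long follow-up: "Patients who discontinue ADT therapy will continue to be followed for safety outcomes". The reason given there is to assess the long-term safety of ADT.
- Section 6 says "All analyses will be performed on the actual (received) treatment", but does not say whether an event or person-year after a switch goes to the first or the second drug. Section 10.1.1 does not say which periods its person-years cover.

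**The concern.** The purpose stated in Section 8 covers treatment-emergent events in general, but the definition in Section 10.2 removes the restriction for every general table while Section 10.1.1 keeps the test. A patient who stopped Firmagon two years earlier, or who now receives an agonist, can still contribute events to a flagged comparison of the two groups.

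One of the secondary objectives in Section 2.1 is to identify unrecognised adverse drug reactions. For events outside the AESI list, the general tables are the main between-group comparison in the plan. A flag there can be missed, or can appear falsely, because of what happened after the initial treatment ended.

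**Working it through.** **1. Person-years and the plan's own figure.** Section 3.2 gives 1,000 and 500 patients, 5 years, and 10% dropout spread uniformly. Firmagon: 1,000 × (0.9 × 5 + 0.1 × 2.5) = 4,750 person-years. Agonist: 500 × 4.75 = 2,375. At 5.00 per 100 person-years, Firmagon has 237.5 expected events, and the exact Poisson 95% interval is 4.38 to 5.68, as in Table 2. All eight rows of Table 2 agree within 0.03. Table 2 is not in question; it only confirms the person-year base.

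**2. Rates.** Section 3.2 gives serious cardiovascular rates of 5 (Firmagon) and 8 (agonist) per 100 person-years from the one-year Phase 3 study. The ratio is 5/8 = 0.625. These are AESI rates; they stand in here for any event in a general table.

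**3. Equal shares after the main period.** Let f be the share of person-time after the main period. The SAP gives no value, so f is assumed. Pooled rate per arm = (1 − f) × main-period rate + f × later rate. Take a later rate of 8 in both arms, with events kept under the first drug. Power is for a two-sided 5% Wald test on the log rate ratio, SE = √(1/E₁ + 1/E₂), where E₁ and E₂ are the expected events per arm. This approximates the exact test in Section 10.1.1.

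| f | Firmagon pooled rate | Pooled ratio | Power, all periods | Power, main period only |
|---|---|---|---|---|
| 10% | 5.3 | 0.66 | 0.99 | 0.996 |
| 20% | 5.6 | 0.70 | 0.96 | 0.99 |
| 30% | 5.9 | 0.74 | 0.90 | 0.98 |
| 50% | 6.5 | 0.81 | 0.62 | 0.93 |

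For f = 50%, all periods: events are 4,750 × 0.065 = 308.75 and 2,375 × 0.08 = 190; SE = 0.092; |ln 0.8125| = 0.208; z = 2.25; power 0.62. Main period only: 118.75 and 95 events; SE = 0.138; |ln 0.625| = 0.470; z = 3.41; power 0.93.

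To place f: if ADT is changed or stopped at a constant rate g over 5 years, the main-period share is (1 − e^(−5g))/(5g). For g = 0.1, 0.2 and 0.3 per year this is 0.787, 0.632 and 0.518, so f is 21%, 37% and 48%. These rates are assumptions too.

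**4. Some later time on the same drug.** A regimen change can end the main period while the drug stays the same. If half the later Firmagon time keeps the rate of 5 (assumed), f = 20% gives (0.9 × 5 + 0.1 × 8)/8 = 0.66, and f = 50% gives (0.75 × 5 + 0.25 × 8)/8 = 0.72.

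**5. Unequal shares.** All inputs here are assumed except the main-period rates.
- No on-drug difference (5 in both arms), later rate doubled to 10. With f = 40% for Firmagon and 20% for agonist, the ratio is 7/6 = 1.17 and the probability of a flag is about 0.34 instead of 0.05. With the shares reversed, it is 6/7 = 0.86 and about 0.35.
- On-drug ratio 0.625, later rate 16 in both arms. With f = 10% for Firmagon and 40% for agonist: (4.5 + 1.6)/(4.8 + 6.4) = 6.1/11.2 = 0.55, exaggerated. With 40% and 10%: (3.0 + 6.4)/(7.2 + 1.6) = 9.4/8.8 = 1.07, reversed.

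**The case against.** The best defence is that the SAP uses a broad treatment-emergent definition for reporting and applies the period restriction where it plans its main comparison. Section 8 opens with AESIs, Section 8.1 closes by saying that main-period AESIs make the comparison more valid, and Section 10.4.1 carries this out. The comparative secondary objective names AESIs only. Late events are collected on purpose (Section 3.1), and recognition of adverse drug reactions also rests on investigator causality and narratives (Section 10.3).

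Much of this stands. The AESI analyses are sound on this point, and reporting late events is right. It does not justify the flag: Section 8 names treatment-emergent events without limiting them to AESIs, and Section 10.1.1 tests the pooled periods.

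A reader might infer that true differences will simply be diluted. The documents do not support that as a certainty. Dilution needs similar later rates in both arms and events kept with the first drug, and Section 6 leaves that attribution open. A reader might also take all later time as time off the drug, but Sections 8 and 8.1 end the main period at a regimen change that may keep the same drug. Nor is every later event counted: for patients without an end-of-trial visit, Section 10.3 stops at 45 days after the last visit.

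**Conclusion.** The point holds as a conflict between the purpose in Section 8 and the flagged general tables built on Section 10.2. Those comparisons may be biased. Under equal shares, alike later rates and attribution to the first drug, a ratio of 0.625 moves to 0.70 at 20% and 0.81 at 50% later person-time. It moves less if part of that time is on the same drug. With unequal stopping or switching, a difference can be created, exaggerated or reversed. Every share and later rate used is an assumption, so the true size and direction are unknown. The consequence is limited to the general adverse event tables and should be corrected there; the AESI analyses are not touched.

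**What to change.** In Sections 10.1.1 to 10.3.2, state that incidence rates and significance flags in the general TEAE tables use Main Treatment Period events and Main Treatment Period person-years. Keep all later events, as Section 3.1 intends, in descriptive tables without flags. Split these by treatment then received (same drug with changed regimen, other ADT, no ADT), each with its own person-years. This also settles the attribution and denominator that Sections 6 and 10.1.1 leave open.

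The cost is SAP wording and one further set of tables. The flagged comparison will have fewer events; delayed events and intermittent exposure to the same drug will appear only descriptively. Ending person-time at a stop or change may itself be informative, so the table should carry that caution.

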### **10.3 Treatment-Emergent Adverse Events**

Treatment-emergent adverse events will be classified according to the MedDRA version 15.0 or later. All AEs will be reported.

Adverse events will be classified according to their intensity (using CTCAE v4.02) and relationship to the IMP according to investigator assessment. The number of patients with each AE will be displayed by SOCs (alphabetically) and PT (in decreasing frequency of occurrence).

For patients without an EOT Visit (e.g. due to death), adverse events will be considered treatment emergent if the event occurs within 45 days after the last visit for the patient.

Written narratives will be issued for all serious AEs and AEs leading to withdrawal.

Missing values will be treated as missing, except for causality of AEs to trial drug. If causality is missing, the AE will be regarded as possibly related to trial drug. Related AEs (judged as being reasonably possibly related to trial drug) will be termed ADRs.

### **10.3.1 Overview of Treatment-Emergent Adverse Events**

An AE overview summary table will be prepared for the following categories:

- All AEs
- Deaths
- Serious AEs
- Severe AEs (CTCAE grade 3-5)
- AEs leading to withdrawal

### **10.3.2 Incidence of Adverse Events**

Summary tables of TEAEs by MedDRA SOC (alphabetically) and PT (in decreasing frequency of occurrence) will be prepared for:

- All AEs
- Common AEs (at least 5% of patients)
- AEs by causality
- AEs by intensity
- Serious AEs
- AEs leading to withdrawal
- Non-serious AEs (at least 5% of patients)

Supporting data listings will be provided for:

- All AEs sorted by patient number
- All AEs sorted by MedDRA SOC and PT
- Serious AEs
- AEs leading to death
- AEs leading to withdrawal

## 10.4 Adverse Events of Special Interest (AESI)

An AESI is a subgroup of general TEAEs and as such are classified and treated as described in Section 10.3.

### 10.4.1 Definition

The main objective of this observational study is to collect information on AESI. Specifically: cardiovascular events; new onset of diabetes mellitus; progression of osteoporosis or osteopenia; events associated with bone fractures (osteonecrosis); and all-cause mortality. The worsening of glucose intolerance based on lab data has been described in Section 9.1.5. Only events classified as serious will be considered.

Any AESI in the medical history occurring during the “Main Treatment Period” (or thereafter), or any adverse event of special interest in the adverse event report log occurring during the “Pre-consent Period” will be listed, as these possibly should be shifted from medical history to adverse event (or opposite).

In order to limit bias from different treatment effects and overlapping treatment periods and to make data comparable to a greater degree *only* AEs reported during the “Main Treatment Period” are considered (see Section 8.1 for details).

The AEs will be coded using MedDRA lowest level term (LLT). An AE included in any of the following Standardised MedDRA queries (SMQs), at the narrow search scope level, is defined as an event of special interest:

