## 2 Study Objectives and Endpoints

### 2.1 Objectives

#### Primary Objective

The primary objective of this observational study is to describe the risk of the following Adverse Event of Special Interest (AESI) in association with Firmagon treatment:

- Cardiovascular events
- Events related to decreased bone density, including new onset or progression of osteoporosis or osteopenia, and fractures
- New onset or exacerbation of glucose intolerance or type 2 diabetes mellitus
- Changes in hepatic enzyme levels

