### 2.2 Endpoints

#### Safety Endpoints

The following endpoints will be analysed in the study:

1. Rate of AESI
  - a. Incidence rate of cardiovascular events
  - b. Incidence rate of bone fracture, including osteoporotic/fragility fractures
  - c. Incidence rate of new onset or worsening osteoporosis or osteopenia

- d. Incidence rate of new-onset diabetes mellitus
  - e. Incidence rate of all-cause mortality
2. Occurrence of relevant laboratory value changes
- a. Changes in hepatic enzymes, fasting serum glucose, testosterone and PSA levels
  - b. Incidence rate of glucose intolerance

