#### **9.1.4 Change in Fasting Serum Glucose and Serum Hepatic Enzymes from Baseline to Each Visit**

Change and percentage change from baseline in glucose and hepatic enzyme levels (alanine aminotransferase, aspartate aminotransferase, bilirubin and alkaline phosphatase) will be summarised by descriptive summary statistics for each treatment arm (median and inter-quartile range) as well as actual values by visit and treatment arm for the analyses set.

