### **9.1.5 Incidence of Glucose Intolerance (Impaired Fasting Glycaemia)**

The protocol defines glucose intolerance as a fasting glucose level of 6.1-6.9 mmol/L (110mg/dl-125 mg/dL). (This corresponds to WHO's definition of impaired fasting glycemia [8].) The incidence rate of glucose intolerance will be analysed and presented as described in Section 10.5.1. Adjusting factors will be age, stage of disease and history of diabetes mellitus (as reported by the patient).

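### The primary objective includes exacerbation of glucose intolerance or diabetes, but Section 9.1.5, cited for worsening, has no worsening rule and can count improved or unchanged patients as incident

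*SAP*

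**What the plan says.** Section 2.1 lists, among the risks to be described for Firmagon, "New onset or exacerbation of glucose intolerance or type 2 diabetes mellitus". In Section 2.2 the matching diabetes endpoint is "Incidence rate of new-onset diabetes mellitus", and a separate laboratory endpoint is the incidence rate of glucose intolerance.

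Section 10.4.1 defines the events of special interest: "Specifically: cardiovascular events; new onset of diabetes mellitus; progression of osteoporosis or osteopenia", followed by bone events and mortality. It adds that "The worsening of glucose intolerance based on lab data has been described in Section 9.1.5" and that "Only events classified as serious will be considered". The diabetes event is identified by the narrow scope of the hyperglycaemia/new onset diabetes SMQ.

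Section 9.1.5 gives the laboratory rule: "The protocol defines glucose intolerance as a fasting glucose level of 6.1-6.9 mmol/L". The rate is analysed as in Section 10.5.1, and "Adjusting factors will be age, stage of disease and history of diabetes mellitus (as reported by the patient"). The output listed in 10.5.1 is a rate per arm and a rate ratio.

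Section 9.1.4 summarises "Change and percentage change from baseline in glucose and hepatic enzyme levels" by treatment arm and visit.

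**The concern.** Exacerbation of diabetes can occur only in someone who already has it. After Section 2.1 the SAP does not carry it forward, although for bone it does carry worsening into the endpoint list and the SMQ definition. Section 12, which lists deviations from the protocol analysis, does not mention the change.

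The cross-reference in 10.4.1 suggests that 9.1.5 supplies the worsening part. It does not. It is a band rule on a single value, with no comparison to baseline, no direction of change and nothing above 6.9 mmol/L. Because diabetes history is an adjusting factor, known diabetics must be in the model. A covariate can absorb a different event rate in diabetics. It cannot change what an event means for them, and a diabetic who enters the band from above has improved.

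Two things are at stake. One named part of a descriptive primary objective has no defined result in the SAP. And the 9.1.5 rate, presented as incidence, can mix new impaired glycaemia with patients who improved or did not change.

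**Working it through.** **1. The rule applied to example paths.** Input: the 6.1-6.9 mmol/L band of Section 9.1.5. The first value is the baseline, the second is the only follow-up value, and the event test is 6.1 ≤ follow-up ≤ 6.9.

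| Patient | Path (mmol/L) | Change | Counted? |
|---|---|---|---|
| No diabetes | 5.5 to 6.5 | worse | yes |
| No diabetes | 5.5 to 7.5 | worse | no |
| In band at baseline | 6.5 to 7.4 | worse | no |
| In band at baseline | 6.5 to 6.3 | not worse | yes |
| Known diabetic | 8.0 to 11.0 | worse | no |
| Known diabetic | 7.4 to 6.5 | better | yes |

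The rule works for a normoglycaemic patient who enters the band. It fails as a worsening rule for the patients to whom exacerbation applies. If an in-band value is recorded at an earlier follow-up visit, that value counts in its own right. The misses apply when none is recorded.

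**2. Does the count run against harm in diabetics?** The SAP gives no glucose distribution, so the inputs are assumed: normally distributed patient means, visit noise SD 0.7 or 1.0, and follow-up of 5 years without dropout. Visits are 3-monthly to year 2 and then 6-monthly, or 6-monthly throughout. Rate = 100 × patients with a rounded value in the band ÷ total time to the first such value or 5 years.

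For mean glucose 7.5-9 (between-patient SD 1.5 to 2), over all 16 combinations, the rates per 100 patient-years are:
- improved by 1 mmol/L: 12-42
- stable: 7-32
- worse by 1: 3.5-16.5
- worse by 2: about 1-7

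Within each setting, better control raises the count and worse control lowers it.

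At lower means (3-monthly then 6-monthly visits) this order breaks:
- Mean 7.0, SD 1.5: stable and improved by 1 are equal (about 30 at noise 0.7, about 39 at noise 1.0).
- Mean 6.5, SD 1.0: stable 61-71; improving by 1 lowers it to about 33-44, and worsening by 1 also lowers it.
- Mean 5.8, SD 0.8: stable 54-66; worsening by 1 raises it to 77 or more, and improving by 1 lowers it to 14-24.

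The direction therefore depends on glucose level.

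**3. What precision would a result in known diabetics have?** First, the SAP's own diabetes figure. Patient-years = 1000 × (0.9 × 5 + 0.1 × 2.5) = 4750. Events = 2.90 × 47.5 = 137.75, rounded to 138. The exact Poisson 95% CI is 2.44-3.43, against 2.44-3.45 in Table 2, so the inputs are understood.

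For a diabetic subgroup, assume that 10-25% of each arm is diabetic. Mean time to first event or dropout is the integral over 0-5 years of exp(-rt)(1 - 0.1t/5). This gives 4.427 years at r = 0.029 and 3.754 at r = 0.10. The 2.9 per 100 patient-years is the SAP's new-onset rate, borrowed for scale; the rate of 10 is assumed.

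- At 2.9 and 10% diabetic: Firmagon 100 × 4.427 × 0.029 = 12.8 events; GnRH agonist 50 × 4.427 × 0.029 = 6.4. Rate-ratio CI factor = exp(1.96 × √(1/12.8 + 1/6.4)) = 2.6.
- At 10 and 25% diabetic: Firmagon 250 × 3.754 × 0.10 = 93.9; GnRH agonist 46.9. Factor = exp(1.96 × √(1/93.9 + 1/46.9)) = 1.4.
- If the Main Treatment Period ends at 2 years, the factors range from 1.7 to 4.2.

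This is usable for description within an arm and weak for comparing arms.

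**The case against.** The objective names one combined item for the treated population and asks for no rate confined to diabetics. Describing it in everyone, adjusted for diabetes history, is a legitimate reading. This stands: a separate diabetic rate is not something the objective strictly demands. It does not rescue 9.1.5, which lacks a worsening rule in any population.

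A reader might infer that exacerbation is captured nowhere. The documents do not support that. Section 9.1.4 summarises glucose at every level. Reported events reach the adverse event tables (10.3.2), the glucose-intolerance overview (10.4.3) and the SMQ tables (10.4.4). A serious event in a known diabetic that codes to the narrow SMQ would also enter the diabetes model. The SAP describes all of these by arm, not by diabetes history. The table specification is a separate document (Section 14) and may add such a split, so its absence cannot be proved.

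The band is attributed to the protocol and defines impaired fasting glycaemia, so values above 6.9 lie outside that condition by design. That is fair, and the band should stay. The problem is who is at risk, and that 10.4.1 cites the section for worsening.

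It can also be said that incidence implies a normal baseline. No such condition is written, and the diabetes-history covariate points the other way.

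**Conclusion.** The point holds on the text and deserves correction. Exacerbation is in the primary objective, the endpoints and event definition carry only new-onset diabetes, and the section cited for worsening does not define it. As written, 9.1.5 can count a known diabetic who improves into the band, or a patient already in it at baseline. It adds no event for a move from 6.5 to 7.4 or from 8.0 to 11.0. These statements need no assumptions beyond a literal reading of the rule.

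The size is not determined. It is tempting to say that the count falls as diabetics get worse. In the simulations that holds at mean levels of about 7.5 mmol/L or more and not reliably below, and the SAP gives no glucose levels or share of diabetics. No general direction, and no effect on the planned rate ratio, should be claimed. The sample-size figures are unaffected.

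**What to change.** 1. In 9.1.5, restrict the at-risk set to patients without a history of diabetes (Section 7.6.2.1) and without a known baseline fasting glucose of 6.1 mmol/L or above. State how missing baselines are handled, since Section 7 sets them to missing for Firmagon patients already on treatment at the baseline visit. Drop the diabetes-history covariate there, keep the 6.1-6.9 band, and record the change in Section 12.
2. Present the 9.1.4 glucose change by diabetes history and arm, with the number moving from 6.9 or below to above 6.9 mmol/L, as the descriptive exacerbation result. Point the worsening sentence in 10.4.1 to it.
3. Optionally, tabulate hyperglycaemia/diabetes SMQ events by arm among patients with a history of diabetes, as supportive and descriptive only. If events of any seriousness are included, say that this departs from the serious-only rule. The SAP gives the SMQ code but not its terms, so check first that worsening of known diabetes falls within it.

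The cost is SAP wording, a line in Section 12 and a few tables from data already collected. The limits should be stated with the results: glucose testing is at the physician's discretion, some Firmagon baselines are missing, diabetes type is not recorded in the yes/no history item, and comparison between arms among diabetics is imprecise.

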### **10.4.3 Overview of Treatment-Emergent Adverse Events Generating an Event of Special Interest**

An overview summary table of TEAEs generating an event of special interest will be prepared for the following categories:

- All AEs
- AEs leading to death
- Serious AEs
- Severe AEs (CTCAE grade 3-5)
- AEs leading to withdrawal

This table will be prepared for each AESI (cardiovascular event, bone fracture, and glucose intolerance).

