## 10.5 Analyses of Adverse Events of Special Interest

### 10.5.1 Primary Analysis of Adverse Events of Special Interest (AESI)

The mortality rate and respective incidence rates (number of AEs per 100 person years) of each AESI will be estimated using a Poisson regression model. In general, assuming a constant incidence rate of  $\lambda_{i,j}$  per unit time for a category  $i$ , treatment  $j$  ( $=0$  for GnRH agonist and 1 for Firmagon), the number of events  $y_{i,j}$  observed during a time interval of length  $t_{i,j}$  (unit 100 years) is distributed as Poisson with mean  $\mu_{i,j}=\lambda_{i,j}t_{i,j}$ . The mean of a Poisson distributed variable is modelled by

$$\log \mu_{i,j} = \log \lambda_{i,j} - \log t_{i,j} = \alpha + \beta_j + \beta_{i,j} x_{i,j},$$

where  $t_{i,j}$  is the number of person years, and  $\log(t_{i,j})$  is modelled as the “offset” with regression coefficient equal to one. Besides the effects of intercept ( $\alpha$ ) and treatment, modelled by  $\beta_j$  (with GnRH agonist as reference; e.g.  $\beta_0=0$ ), the incidence rate (mean) is driven by the adjusting factors for the present category. By this, the adjusted incidence rate ratio (IRR) of an incidence for patients on Firmagon as compared to GnRH agonist is estimated by  $\exp(\beta_i)$ . For more details, please see page 501 of [5], and page 204 of [6].

Table 5 illustrates data from one treatment arm by each category of adjusting factors (age and stage of disease) used in the model. This example may be extended to include more adjusting factors if required.

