## 10.6 Exploratory Cardiovascular Analyses

This section addresses explorative cardiovascular events, defined as Major Adverse Cardiovascular Event (MACE). Analysis will be performed both in the *overall* patient population (Safety Analysis Set), as well as in the *CVD* subgroup, i.e. patients with at least one prior CV event reported in their medical history that was within the *broad* scope search term of any of the five SMQs:

- Myocardial infarction
- Ischaemic cerebrovascular conditions
- Haemorrhagic cerebrovascular conditions
- Embolic and thrombotic events, arterial
- Other ischaemic heart disease

The time to first event for any SAE within the *narrow* scope the five SMQs listed above is defined as the '*time to CV SAE*'. In addition, a combined endpoint defined as '*time to CV SAE or death from any cause*' will be analysed. Note that death itself is not an adverse event, but it may be an outcome of an adverse event.

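### Section 10.4.1 limits AESIs to serious events, a limit absent from the primary objective and endpoints 1a-1d, so the adjusted diabetes and bone results would not estimate the Section 2.2 endpoints

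*SAP*

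**What the plan says.** **The restriction.** SAP Section 10.4.1 names the AESI classes (cardiovascular, diabetes, osteoporosis/osteopenia, bone fracture through osteonecrosis, all-cause mortality) and adds: "Only events classified as serious will be considered". It then confines the AESIs to the Main Treatment Period. Finally it says that an AE in a listed SMQ, "at the narrow search scope level, is defined as an event of special interest".

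**Where it is used.** Section 10.5.1 takes these events into the primary model: the "respective incidence rates (number of AEs per 100 person years) of each AESI will be estimated using a Poisson regression model". Sections 10.5.2 and 10.5.3 use the same events for the log-rank and Cox comparisons.

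**What is to be estimated.** The primary objective in Section 2.1 includes "New onset or exacerbation of glucose intolerance or type 2 diabetes mellitus". Section 2.2 includes "Incidence rate of new onset or worsening osteoporosis or osteopenia" and "Incidence rate of new-onset diabetes mellitus". Neither section mentions seriousness for any AESI class.

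**Planning.** Section 3.2 calls the CS21 cardiovascular rates (5 and 8 per 100 patient-years) serious. It does not describe the diabetes rate (2.90) or the fracture rates (0.6 and 7.91) that way, and these feed Table 2. Section 12, on deviations from the protocol analysis, does not mention the limit.

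**The concern.** The seriousness rule decides what is counted in the primary analysis. Under Section 10.4.1 a patient with a new diagnosis of diabetes or osteoporosis that was not classified as serious contributes no event. The result would nevertheless be reported against an endpoint defined as the incidence of new-onset diabetes, or of new or worsening osteoporosis or osteopenia. The quantity estimated changes, and not only its precision: the reported rate is the endpoint's rate multiplied by the serious share.

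This is a safety study whose primary purpose is to describe these risks, so a serious-only rate under an unrestricted label would read as a lower risk than the one defined. The comparison is affected too. Section 10.5.1 interprets an IRR interval that includes 1 as a failure to establish a difference, and fewer events make that outcome more likely. No adjusted all-event IRR would exist for the diabetes, osteoporosis/osteopenia or bone fracture AE classes.

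**Working it through.** **1. Compare the places that define the event.**

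| Place in SAP | Seriousness limit? |
|---|---|
| 2.1 primary objective | none |
| 2.2 endpoints 1a-1d | none |
| 3.2 CS21 cardiovascular rates | described as serious |
| 3.2 and Table 2, diabetes and fracture rates | not described as serious |
| 10.4.1 | serious only |
| 10.5.1-10.5.3 | use the AESIs of 10.4 |
| 12 | limit not mentioned |

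The sentence in Section 10.4.1 follows the one on laboratory glucose intolerance, but it cannot sensibly apply to that alone. Section 9.1.5 defines glucose intolerance by a glucose value of 6.1-6.9 mmol/L, which is not graded for seriousness. All-cause mortality (endpoint 1e) is unaffected.

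**2. Reproduce the plan's own figure.** Table 2 gives new-onset diabetes as 2.90 (2.44, 3.45). Exact binomial (Clopper-Pearson) limits on 1000 × 5 × 0.9 = 4,500 patient-years reproduce this: 0.0290 × 4,500 = 130.5, rounded up to 131 events, gives 2.44 to 3.45. The same method reproduces the other seven rows to two decimals. The printed diabetes precision therefore belongs to the full 2.90 rate, with no reduction for seriousness.

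**3. Illustrate the effect for diabetes.** Inputs from Section 3.2: 1,000 Firmagon and 500 agonist patients, 5 years, 10% dropout uniform over time, 2.90 per 100 patient-years (an agonist rate that Table 2 assumes for Firmagon). Assumed, because the SAP does not give it: serious share *f* = 0.75, 0.50 or 0.10.

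Section 10.4.2 counts the first event only, so for hazard *h* per year:

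- Patient-years = 1000 × ∫₀⁵ (1 − 0.02t) exp(−*h*t) dt
- Firmagon events = *h* × patient-years; agonist events = half of that
- 95% factor for the IRR, at a true IRR of 1 = exp(1.96 × √(1/E_F + 1/E_A)), with E_F and E_A the events in the two groups

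With all events, *h* = 0.029. The integral is 4.654 − 0.02 × 11.355 = 4.427, so there are 4,427 patient-years and 0.029 × 4,427 = 128.4 events. With serious events only, *h* = 0.029*f*, and a patient with only a non-serious event stays at risk.

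| Share *f* | Rate per 100 PY | Firmagon PY | Firmagon events | Agonist events | IRR factor (×/÷) |
|---|---|---|---|---|---|
| All events | 2.90 | 4,427 | 128.4 | 64.2 | 1.35 |
| 0.75 | 2.18 | 4,505 | 98.0 | 49.0 | 1.41 |
| 0.50 | 1.45 | 4,585 | 66.5 | 33.2 | 1.52 |
| 0.10 | 0.29 | 4,716 | 13.7 | 6.8 | 2.50 |

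These are not forecasts. The Main Treatment Period ends at a change or discontinuation of ADT (Section 8.1), so real exposure may be shorter, and the true event rate may differ from 2.90.

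**4. No counts for the bone classes.** Section 10.4.1 defines the fracture class by the Osteonecrosis SMQ, for which the SAP gives no rate. Osteoporosis/osteopenia has no planning rate either.

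**The case against.** **The operational rule is explicit.** Section 10.4.1 can be read as filters applied in turn: serious, Main Treatment Period, narrow SMQ. This stands. A reader might infer that the SMQ sentence, or the AE-based unit in Section 10.5.1, contradicts the limit. Neither does: a later sentence that does not repeat a filter does not cancel it, and a serious AE is still an AE. The conflict is with Sections 2.1 and 2.2.

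**The overview table.** Section 10.4.3 says "An overview summary table of TEAEs generating an event of special interest will be prepared for the following categories", and these include separate rows for all AEs and serious AEs. A reader might infer that non-serious AESIs were intended. Section 10.6.1 reuses that table for an endpoint built from "The time to first event for any SAE within the" five listed SMQs, which is serious by definition. The rows show a standard shell, not intent.

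**Non-serious events are not lost.** This stands in part. Section 10.1.1 provides crude rates with an exact test, and Section 10.3.2 tabulates all AEs by SOC and PT. Section 9.1.5 sends laboratory glucose intolerance to the adjusted model with no seriousness filter. None of these gives an adjusted all-event IRR for the diabetes or bone AE classes.

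**Serious-only may be deliberate.** For cardiovascular events the CS21 planning rates support that. Section 3.1 also notes that Firmagon is dosed monthly while agonists may be given less often, so non-serious events could be detected more readily on Firmagon. These are reasons a sponsor could give for the limit, but the SAP does not give them, and they do not make the endpoint labels correct.

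**A departure from the protocol.** A reader might infer one from the silence of Section 12. The protocol is not at hand, so this is not established.

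**Conclusion.** The concern holds as a mismatch between Section 10.4.1 and Sections 2.1 and 2.2, and it should be resolved before the analysis is run. If the SAP is followed, the adjusted rates, IRRs, Kaplan-Meier and Cox results for new-onset diabetes, osteoporosis/osteopenia and the bone fracture class are serious-only and do not estimate the endpoints as named. The Table 2 precision for diabetes and fracture rests on rates not described as serious, so it cannot be taken to apply to serious-only endpoints.

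The size depends on a serious share that the SAP does not give. A reader might infer a severe loss of precision, but the documents do not establish one: for diabetes the IRR factor moves only from 1.35 to 1.41 at an assumed 75% share, and reaches 2.50 at 10%. The definitional point rests on none of these assumptions. Defining fracture through the Osteonecrosis SMQ is a separate matter.

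**What to change.** State one seriousness rule for each AESI class and make Sections 2.1, 2.2, 10.4.1 and 10.5.1 agree. Serious-only may stay for cardiovascular events if endpoint 1a says so. For diabetes and the bone classes the sponsor should choose one of two routes:

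- **(a) Remove the limit.** The primary analysis then uses all narrow-SMQ events in the Main Treatment Period. A serious-only sensitivity analysis is optional.
- **(b) Keep the limit.** Relabel endpoints 1b-1d as serious events, state that the Table 2 diabetes and fracture precision does not apply to them, declare the limit in Section 12 if it departs from the protocol, and add the all-event adjusted IRR as a supporting analysis.

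The cost is some rewording and at most one extra set of AESI tables, from AEs already collected and coded. Under (a), the drawback is possible over-detection of non-serious events with monthly Firmagon visits. The optional serious-only analysis would help show whether that drives the IRR.
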